**Note: Non-irAE will be managed as appropriate, following clinical practice recommendations.**

a AST/ALT: >3.0 to 5.0 x ULN if baseline normal; >3.0 to 5.0 x baseline, if baseline abnormal; bilirubin:>1.5 to 3.0 x ULN if baseline normal; >1.5 to 3.0 x baseline if baseline abnormal

b AST/ALT: >5.0 to 20.0 x ULN, if baseline normal; >5.0 to 20.0 x baseline, if baseline abnormal; bilirubin:>3.0 to 10.0 x ULN if baseline normal; >3.0 to 10.0 x baseline if baseline abnormal

c AST/ALT: >20.0 x ULN, if baseline normal; >20.0 x baseline, if baseline abnormal; bilirubin: >10.0 x ULN if baseline normal; >10.0 x baseline if baseline abnormal

d The decision to withhold or permanently discontinue pembrolizumab is at the discretion of the investigator or treating physician. If control achieved or ≤ Grade 2, pembrolizumab may be resumed.

e Events that require discontinuation include, but are not limited to: encephalitis and other clinically important irAEs (e.g., vasculitis and sclerosing cholangitis).

### **5.2.3 Dose Modification and Toxicity Management of Infusion-Reactions Related to Pembrolizumab**

Pembrolizumab may cause severe or life-threatening infusion-reactions, including severe hypersensitivity or anaphylaxis. Signs and symptoms usually develop during or shortly after drug infusion and generally resolve completely within 24 hours of completion of infusion. Dose modification and toxicity management guidelines on pembrolizumab associated infusion reaction are provided in Table 5.5.

**Table 5.5 Pembrolizumab Infusion Reaction Dose modification and Treatment Guidelines**

NCI CTCAE Grade	Treatment	Premedication at Subsequent Dosing

Grade 1 Mild reaction; infusion interruption not indicated; intervention not indicated
	
Increase monitoring of vital signs as medically indicated until the participant is deemed medically stable in the opinion of the investigator.
	
None

Grade 2 Requires therapy or infusion interruption but responds promptly to symptomatic treatment (e.g., antihistamines, NSAIDs, narcotics, IV fluids); prophylactic medications indicated for ≤24 hrs
	
Stop Infusion. Additional appropriate medical therapy may include but is not limited to: IV fluids Antihistamines NSAIDs Acetaminophen Narcotics Increase monitoring of vital signs as medically indicated until the participant is deemed medically stable in the opinion of the investigator. If symptoms resolve within 1 hour of stopping drug infusion, the infusion may be restarted at 50% of the original infusion rate (e.g., from 100 mL/hr to 50 mL/hr). Otherwise dosing will be held until symptoms resolve, and the participant should be premedicated for the next scheduled dose. Participants who develop Grade 2 toxicity despite adequate premedication should be permanently discontinued from further study drug treatment
	
Participant may be premedicated 1.5h (± 30 minutes) prior to infusion of pembrolizumab with: Diphenhydramine 50 mg po (or equivalent dose of antihistamine). Acetaminophen 500-1000 mg po (or equivalent dose of analgesic).


Grades 3 or 4 Grade 3: Prolonged (i.e., not rapidly responsive to symptomatic medication and/or brief interruption of infusion); recurrence of symptoms following initial improvement; hospitalization indicated for other clinical sequelae (e.g., renal impairment, pulmonary infiltrates) Grade 4: Life-threatening; pressor or ventilatory support indicated
	
Stop Infusion. Additional appropriate medical therapy may include but is not limited to: Epinephrine** IV fluids Antihistamines NSAIDs Acetaminophen Narcotics Oxygen Pressors Corticosteroids Increase monitoring of vital signs as medically indicated until the participant is deemed medically stable in the opinion of the investigator. Hospitalization may be indicated. **In cases of anaphylaxis, epinephrine should be used immediately. Participant is permanently discontinued from further study drug treatment.
	
No subsequent dosing

Appropriate resuscitation equipment should be available at the bedside and a physician readily available during the period of drug administration. For further information, please refer to the Common Terminology Criteria for Adverse Events v5.0 (CTCAE) at http://ctep.cancer.gov
		

### Other allowed dose interruption for pembrolizumab

Pembrolizumab may be interrupted for situations other than treatment-related AEs such as medical/surgical events or logistical reasons not related to study therapy. Participants should be placed back on study therapy within 3 weeks of the scheduled interruption unless otherwise discussed with the Sponsor. The reason for interruption should be documented in the patient's study record.

### **5.2.4 Second Course**

All participants who stop study treatment with SD or better may be eligible for up to an additional 17 cycles (approximately 1 year) of pembrolizumab treatment if they progress after stopping study treatment from the initial treatment phase. This retreatment is termed the Second Course Phase of this study and is only available if the study remains open, and the participant meets the following conditions:

#### **EITHER**

- Stopped initial treatment with study treatment after attaining an investigator-determined confirmed CR based on RECIST 1.1, and
  - Was treated with at least 8 cycles of study treatment before discontinuing treatment, and
  - Received at least 2 treatments with pembrolizumab beyond the date when the initial CR was declared

#### **OR**

- Had SD, PR, or CR and stopped study treatment after completion of 35 administrations (approximately 2 years) of study treatment for reasons other than disease progression or intolerability

#### **AND**

- Experienced an investigator-determined radiographic disease progression by RECIST 1.1 after stopping initial treatment, and
  - Upon unblinding at the time of centrally verified disease progression were found to have received pembrolizumab, and
  - No new anticancer treatment was administered after the last dose of study treatment, and
  - The participant meets all of the safety parameters listed in the inclusion criteria and none of the safety parameters listed in the exclusion criteria, and
  - The study is ongoing

An objective response or disease progression that occurs during the Second Course Phase for a participant will not be counted as an event for the primary analysis of either endpoint in this study.

*Note: patients must have measurable disease at the start of protocol treatment to be eligible for this provision.*

## 5.2.5 Monitoring and Toxicity Management

Each patient receiving pembrolizumab in combination with Tamoxifen and Vorinostat will be evaluable for safety. The safety parameters include all laboratory tests and hematological abnormalities, physical findings, and spontaneous reports of adverse events reported to the investigator by patients.

Each patient will be assessed periodically for the development of any toxicity as outlined in [Section 6 Study Procedures and Observations](#). Toxicity will be assessed according to the NCI CTCAE v5.0. Dose adjustments will be made according to the system showing the greatest degree of toxicity.

### 5.2.5.1 Events of Clinical Interest

Selected non-serious and serious adverse events are also known as Events of Clinical Interest (ECI) and must be reported to the Sponsor.

For the time period beginning when the consent form is signed until treatment allocation/randomization, any ECI, or follow up to an ECI, that occurs to any subject must be reported within 24 hours to the Sponsor if it causes the subject to be excluded from the trial, or is the result of a protocol-specified intervention, including but not limited to washout or discontinuation of usual therapy, diet, placebo treatment or a procedure.

For the time period beginning at treatment allocation/randomization through 30 days following cessation of treatment if the subject initiates new anticancer therapy, whichever is earlier, any ECI, or follow up to an ECI, whether or not related to the Sponsor's product, must be reported within 24 hours to the Sponsor, either by electronic media or paper. Electronic reporting procedures can be found in the EDC data entry guidelines. Paper reporting procedures can be found in the Investigator Trial File Binder (or equivalent).

Events of Clinical Interest for this trial include:

1. an overdose of Sponsor's product, as defined in Section 7.3.7 - Definition of an Overdose for This Protocol and Reporting of Overdose to the Sponsor, that is not associated with clinical symptoms or abnormal laboratory results.
2. an elevated AST or ALT lab value that is greater than or equal to 3X the upper limit of normal and an elevated total bilirubin lab value that is greater than or equal to 2X the upper limit of normal and, at the same time, an alkaline phosphatase lab value that is less than 2X the upper limit of normal, as determined by way of protocol-specified laboratory testing or unscheduled laboratory testing.\*

*\*Note: These criteria are based upon available regulatory guidance documents. The purpose of the criteria is to specify a threshold of abnormal hepatic tests that may require an additional evaluation for an underlying etiology. The trial site guidance for assessment and follow up of these criteria can be found in the Investigator Trial File Binder (or equivalent).*

## 5.3 Stopping Rules

There is a futility early stopping built-in within each treatment arm. For Arm A (vorinostat + TAM + pembro): In the first stage, 13 patients will be accrued. If there are 2 or fewer responses in these 13 patients, the study will be stopped. For Arm B (pembro and TAM): In the first stage, 11 patients will be accrued. If there are 1 or fewer responses in these 11 patients, the study will be stopped.

### Clinical Criteria for Early Trial Termination

1. Early trial termination will be the result of the criteria specified below:
2. Quality or quantity of data recording is inaccurate or incomplete
3. Poor adherence to protocol and regulatory requirements
4. Incidence or severity of adverse drug reaction in this or other studies indicates a potential health hazard to subjects
5. Plans to modify or discontinue the development of the study drug

In the event of Merck decision to no longer supply study drug, ample notification will be provided so appropriate adjustments to subject treatment can be made.

### **5.4 Discontinuation and Withdrawal**

Participants may discontinue study treatment at any time for any reason or be dropped from the study treatment at the discretion of the investigator should any untoward effect occur. In addition, a participant may be discontinued from study treatment by the investigator or the Sponsor if study treatment is inappropriate, the trial plan is violated, or for administrative and/or other safety reasons. Specific details regarding procedures to be performed at study treatment discontinuation are provided in Section 6.3.2.6 – Study Procedures Restaging or Off-Study Visit.

A participant must be discontinued from study treatment but continue to be monitored in the study for any of the following reasons:

- The participant or participant's legally acceptable representative requests to discontinue study treatment
- Confirmed radiographic disease progression outlined in Section 3.5.
- Any progression or recurrence of any malignancy, or any occurrence of another malignancy that requires active treatment
- Unacceptable adverse experiences, as described in Section 7.3.5.
- The participant has a medical condition or personal circumstance which, in the opinion of the investigator and/or sponsor, placed the participant at unnecessary risk from continued administration of study treatment.
- The participant has a confirmed positive serum pregnancy test
- Noncompliance with study treatment or procedure requirements
- Recurrent Grade 2 pneumonitis
- Discontinuation of treatment may be considered for participants who have attained a confirmed complete response (CR) and have been treated for at least 8 cycles (at least 24 weeks), receiving [for monotherapy: at least 2 doses of pembrolizumab; for combination treatment: 2 cycles of the combination including 2 doses of pembrolizumab and at least 80% of the planned doses of vorinostat beyond the date when the initial CR was declared. These participants may be eligible for second-course treatment described in Section 5.3.

- The participant is lost to follow-up
- Completion of 35 treatments (approximately 2 years) with pembrolizumab. (Patients may continue vorinostat and tamoxifen.)

Note: The number of treatments is calculated, starting with the first dose. Participants who stop the combination or pembrolizumab after receiving 35 doses may be eligible for retreatment if they progress after stopping study treatment provided they meet the requirements detailed in Section 5.3. Participants may be retreated in the Second Course Phase (Retreatment) for up to an additional 17 cycles (approximately 1 year).

*Note to Author:*

- *Guidance on duration of pembrolizumab for solid tumors:*
  - *When there is disease present on imaging (i.e., metastatic, locally advanced, bulky disease NOS, etc.) – 24 months of pembrolizumab (35 cycles)*
  - *When there is no disease present on imaging (i.e., adjuvant, following resection, maintenance following induction chemo, etc.) – 12 months of pembrolizumab*
- *Guidance on duration of pembrolizumab for hematologic malignancies:*
  - *For widespread, recurrent disease – 24 months of pembrolizumab*

*When using pembrolizumab as consolidative therapy/ limited disease – 12 months.*

A subject must be discontinued from the trial for any of the following reasons:

- The subject or legal representative (such as a parent or legal guardian) withdraws consent.
- Confirmed radiographic disease progression

*Note: For unconfirmed radiographic disease progression, but clear clinical progression in the opinion of the treating physician or investigator, the patient should be withdrawn from study for progression.*

*Note: A subject may be granted an exception to continue on treatment with confirmed radiographic progression if clinically stable or clinically improving by symptoms or tumor markers.*

*Unacceptable adverse experiences as described in Section 7.3.5*

- Intercurrent illness that prevents further administration of treatment
- Investigator's decision to withdraw the subject
- The subject has a confirmed positive serum pregnancy test
- Noncompliance with trial treatment or procedure requirements
- The subject is lost to follow-up

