### **3.6 Duration of Follow Up**

Patients will be followed for 30 days after end of study participation or removal from study. Patients removed from study for unacceptable treatment-related adverse event(s) will be followed until resolution or stabilization of all treatment-related adverse events to Grade 2 or lower.

Subjects who discontinue for reasons other than progressive disease will have post-treatment follow-up for disease status until disease progression, initiating a non-study cancer treatment, withdrawing consent, or becoming lost to follow-up. After documented disease progression, each subject will be followed by telephone for overall survival until death, withdrawal of consent, or the end of the study, whichever occurs first.

Subjects may withdraw consent at any time for any reason or be dropped from the trial at the discretion of the investigator should any untoward effect occur. In addition, a subject may be withdrawn by the investigator or the Sponsor if enrollment into the trial is inappropriate, the trial plan is violated, or for administrative and/or other safety reasons. Specific details regarding discontinuation or withdrawal are provided in Section 5.4.

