### 3.9 Study Completion

The expected study completion date is 48 months after the study opens to accrual.

The study will conclude when all enrolled patients have been followed for more than 30 days following completion of the study. The estimated duration of study, from start of enrollment to final study report is 4 years.

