#### **6.3.3 Survival Follow-up**

After completing the follow-up period, participants will be contacted by telephone every 12 weeks to assess for survival/anti-cancer therapy status until death, withdrawal of consent, or the end of the study, whichever occurs first.

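### Section 5.4 lists five reasons, including confirmed progression, both as stopping treatment only and as leaving the trial; if the second list is followed, overall survival is censored at progression, against Sections 3.6 and 6.3.3

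*Combined protocol and SAP*

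**What the plan says.** Section 5.4 opens its first list with "A participant must be discontinued from study treatment but continue to be monitored in the study for any of the following reasons". The items include "Confirmed radiographic disease progression outlined in Section 3.5", unacceptable adverse experiences, a positive pregnancy test, noncompliance and loss to follow-up.

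Further on, the same section opens a second list with "A subject must be discontinued from the trial for any of the following reasons". Its eight items repeat those five and add withdrawal of consent, intercurrent illness and the investigator's decision. Two notes follow. For clear clinical progression without radiographic confirmation, "the patient should be withdrawn from study for progression". The other reads: "A subject may be granted an exception to continue on treatment with confirmed radiographic progression".

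Other sections keep these patients under follow-up:

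- Section 3.6: after progression, "each subject will be followed by telephone for overall survival until death". Those who stop for other reasons are followed for disease status until progression, new therapy, withdrawal of consent or loss to follow-up. The same section gives a 30-day period after removal from study and points to Section 5.4 for details of withdrawal.
- Section 6.3.3: "participants will be contacted by telephone every 12 weeks to assess for survival/anti-cancer therapy status until death". The calls stop earlier on withdrawal of consent or at the end of the study.
- Section 3.9 expects completion 48 months after opening, and adds: "The study will conclude when all enrolled patients have been followed for more than 30 days following completion of the study".
- Section 2.3 lists overall survival as a secondary endpoint, assessed up to 48 months, with a time frame that refers to deaths on study. Section 8.3.3 summarises it by a Kaplan-Meier median with a confidence interval.
- Sections 8.3.1 and 8.3.2 count all randomized patients. The primary outcome is stable disease or better at 24 weeks. No rule is given for a missing 24-week status.

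**The concern.** Both lists are mandatory, so for the shared reasons staff cannot obey both. The choice decides whether a patient's later data exist.

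Overall survival is most exposed. If participation ends at confirmed progression, survival is censored at an event that strongly predicts death. The Kaplan-Meier estimator assumes that censored patients have the same later hazard as those still at risk. Here those still at risk would be mainly patients without progression, so the curve would be too high and the median could be overestimated or not reached. The reference to deaths on study in Section 2.3 adds to this, because a death after removal might not be counted.

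The second exposure is narrower. A patient taken off the trial before week 24 without progression (for toxicity, pregnancy, noncompliance, illness or the investigator's decision) could have no 24-week status, although Section 3.6 plans to keep following disease status.

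**Working it through.** **Step 1. Compare the lists.**

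| Reason in the trial-exit list | Also in the treatment-only list? | Effect of the conflict |
|---|---|---|
| Confirmed radiographic progression | Yes | Survival follow-up ends or continues |
| Unacceptable adverse experiences | Yes | Disease status and survival end or continue |
| Positive pregnancy test | Yes | Same |
| Noncompliance | Yes | Same |
| Loss to follow-up | Yes | None in practice |
| Withdrawal of consent | No (the other list has a request to stop treatment) | None |
| Intercurrent illness | Not in the same form | Exit conflicts with Section 3.6 |
| Investigator's decision | Not in the same form | Exit conflicts with Section 3.6 |

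Five of eight reasons are in both lists, and four of the five make a practical difference. The note that allows treatment after confirmed progression also conflicts with the mandatory treatment stop in the first list.

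**Step 2. Reproduce the plan's own figures (Section 8.1.1).** With exact binomial sums:

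- Arm A: P(reject) = Σ over x = 3 to 13 of P(X = x; 13, p) × P(Y ≥ 10 − x; 22, p). This gives 0.0249 at p = 0.15 and 0.9036 at p = 0.40 (stated 0.025 and 0.9).
- Arm B: P(reject) = Σ over x = 2 to 11 of P(X = x; 11, p) × P(Y ≥ 7 − x; 19, p). This gives 0.0220 at p = 0.10 and 0.9004 at p = 0.35 (stated 0.025 and 0.9).
- Chance of enrolling 35 + 11 = 46: (1 − 0.0579) × 0.6974 = 0.657 (stated about 65%).
- Between arms, two-sided Fisher test at 0.1, rates 0.4 and 0.1: 72.44% (stated 72.53%).

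The design figures hold and are not in dispute.

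**Step 3. How many could be exposed to censoring at progression by week 24?** On the most likely path, with the assumed rates of 0.40 and 0.10:

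- Arm A: 35 × 0.60 = 21.0
- Arm B: 11 × 0.90 = 9.9
- Total: 30.9 of 46 = 67%

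This is the assumed non-response. It is an upper bound in expectation, because it includes patients who have died or who stopped without progression. It covers week 24 only; later progressions would add to it.

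**Step 4. Is the primary outcome affected?** A patient who progresses before week 24 is a non-responder with a PFS event, so nothing is lost there. Only exits without progression matter. The documents give no rate, so the following is an assumption shown over a range: a share d of would-be responders in each arm has no 24-week status and counts as non-response. The response rate becomes p × (1 − d); for example, 0.40 × 0.90 = 0.36 in Arm A.

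| d | Arm A power (0.40) | Arm B power (0.35) | Between arms (0.40 v 0.10, two-sided Fisher, 0.1) |
|---|---|---|---|
| 0 | 90.4% | 90.0% | 72.4% |
| 5% | 86.4% | 86.8% | 66.7% |
| 10% | 81.2% | 82.7% | 60.8% |
| 15% | 74.7% | 77.7% | 54.7% |
| 20% | 66.8% | 71.7% | 48.5% |

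Arm A expects 35 × 0.40 = 14 responders, so d = 10% is 1.4 patients. The table shows sensitivity, not an expected loss.

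**The case against.** The best defence is that the plan's intention is clear. Sections 3.6 and 6.3.3 require follow-up after progression, and the study calendar has a survival follow-up column. The pointer from Section 3.6 to Section 5.4 closes a paragraph on withdrawal and does not qualify the survival paragraph before it. The second list uses treatment language in places and could be loosely worded off-treatment text. The trial has a single site, overall survival is secondary with no planned test, and no Simon boundary changes. All of this stands, and it lowers the severity. It does not remove the conflict: the second list says trial, not treatment, is mandatory, and sits in the section to which readers are sent.

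A reader might infer more than the documents support:

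- *That survival data will be lost.* This happens only if the second list is followed over Sections 3.6 and 6.3.3.
- *That 67% of patients would be lost.* That figure is assumed non-response, not a loss rate.
- *That progression costs the primary outcome.* Those patients are known non-responders. With all randomized patients in the denominator, a patient without a status can also be read as a non-responder, though no rule says so.
- *That exits would be more frequent in Arm A because of the extra drug.* No comparative rate is given. On the assumed rates, non-response by week 24 is higher in Arm B (90% v 60%), so censoring at progression could be heavier there.
- *That the study closes 30 days after treatment.* Section 3.9 also gives 48 months, matching the overall survival time frame, and its 30 days is a minimum. The sentence is circular and needs tidying, but it does not set an early closure.

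**Conclusion.** The contradiction is real. For five reasons, including confirmed progression, Section 5.4 orders both continued monitoring and removal from the trial, and the second order contradicts Sections 3.6 and 6.3.3. If the second list is applied, overall survival is informatively censored and biased upward, and some patients removed without progression before week 24 could have no 24-week status.

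The size is not known, because the documents give no exit rates. The 31 of 46 bounds exposure by week 24 and rests on the assumed rates of 0.40 and 0.10 and the 35 + 11 path. The power range rests on an assumed loss share. This should be fixed, but it does not undermine the primary decision rule.

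**What to change.** - In Section 5.4, limit the trial-exit list to withdrawal of consent for follow-up and loss to follow-up. All other reasons then end treatment only. Bring the note on clinical progression into line.
- State that patients off treatment without progression keep the disease-status follow-up of Section 3.6 on the existing scan schedule. Scans fall at weeks 9 and 18 and after cycle 9 (9 × 3 = week 27), with none at week 24, so say which scan supplies the 24-week status.
- State that the 12-weekly survival calls of Section 6.3.3 run for all patients to one cut-off consistent with the stated 48 months, and that deaths after treatment ends count for overall survival.
- In the Abstract and Sections 3.6 and 3.9, label the 30-day period as safety follow-up.
- The sponsor must reconcile the note allowing treatment after confirmed progression with the mandatory stop in the first list. No change to when treatment stops is proposed here.

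The cost is an amendment to wording. The calls and disease-status follow-up are already planned; the added work is keeping them open to the cut-off.
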